3. OBJECTIVES AND ENDPOINTS

Objectives	Endpoints
Primary	Primary

To describe the PK profiles of CAB 400 mg/mL formulation following multiple injections administered intramuscularly (gluteus medius or vastus lateralis) or subcutaneously (abdominal) in healthy adult participants
 
To assess the relative bioavailability of a CAB 400 mg/mL formulation administered via different routes (i.e., IM (vastus lateralis), IM (gluteus medius) or SC routes)
 
To compare exposures after CAB 400 mg/mL formulation administered via different routes with historical data of CAB 200 mg/mL formulation administered IM (gluteus medius)
	
Summary measures to include:
 
 • Maximum observed plasma concentration (C_{max}) [Injection 1 and 2] • Time of maximum observed plasma concentration (t_{max}) [Injection 1 and 2] • Area under the concentration – time curve for each injected dose from time zero to last quantifiable time point or 4 weeks following injection whichever is earlier (AUC_{0-t}) • Trough concentrations (C_τ) at 4 weeks following first injection (or earlier if the second injection occurs at <4-week interval) and 4 weeks following the second injection • Apparent terminal phase half-life (t_{1/2}) and absorption rate constant (K_{ALA}) [Injection 2] 
• Pair-wise comparisons of geometric mean ratios of plasma trough concentrations (C_τ), C_{max}, and Plasma AUC_{0-t} [injection phase] for Cohort 1, 2, 3, 4, 4b, and 4h
 
• Geometric mean ratios of plasma trough concentrations (C_τ) for Cohorts 1, 2, 3, 4, 4b, 4h, 5, and 6 (if conducted) compared to historical CAB 200 mg/ml data

Objectives	Endpoints
Safety	Safety

To assess safety and tolerability of CAB 400 mg/mL formulations following repeated intramuscular injections in the gluteus medius, vastus lateralis (lateral thigh) or subcutaneously (abdomen) of healthy adult participants
 
To assess safety and tolerability of CAB 200 mg/mL with rHuPH20 following a subcutaneous (abdominal) injection in healthy adult participants
 
To assess safety and tolerability of CAB 400 mg/mL with rHuPH20 following a subcutaneous (abdominal) injection in healthy adult participants
	
Safety and tolerability parameters including adverse events, clinical laboratory tests, and vital sign assessments

Secondary	Secondary

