8.2.2. Vital Signs

- Vital signs will be measured in a semi-supine position after 5 minutes rest and will include temperature, systolic and diastolic blood pressure, and pulse.

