8.2.6.1. Diary Cards

Participants will complete a diary card following each injection. This allows participants to record and score the severity of any reactions as well as record any action taken such as use of analgesic medication prophylactically or following the injection. Participants will also be asked to collect their temperature daily for 14-days following each injection. Concomitant medication will be recorded in the CRF.

CCI

8.2.6.3.

CCI

CCI

8.2.6.4.

CCI

CCI

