1. INTRODUCTION

The purpose of this reporting and analysis plan (RAP) is to describe the analyses to be included in the Clinical Study Report for Protocol 212482:

Revision Chronology:		
Original protocol	14-Feb-2020	Original
Amendment 1	22-Apr-2020	
Reprioritising the cohorts: the order of Cohorts 2 and 3 has changed, i.e., the subcutaneous (SC) abdominal injection will now be evaluated in Cohort 2 and the intramuscular (IM) lateral thigh injection in Cohort 3; participants will be enrolled sequentially into Cohorts 1, 2, and 3.
 
Adding permissible procedures during the COVID-19 Pandemic.

Amendment 2	26-Jun-2020	
Revisions were made to the study eligibility criteria and safety assessments to further mitigate the potential risks for study conduct during the COVID-19 pandemic.
 
Additional changes were made based on comments and recommendations for revisions of Protocol 212482 received from the FDA's Division of Antivirals as mentioned in the Division's 'Study May Proceed' letter dated 3 June 2020. Changes impacting data collection include: a) clarification that Randomization will occur on Day 1 of the Oral Lead-in (OLI) Phase prior to dosing of oral CAB, b) Participants will have pharmacokinetic (PK) monitoring up to and including Week 52 post their last CAB injection; Participants with undetectable CAB concentrations before Week 52 will be deemed to have completed follow up and return to the clinic for a last study visit at which activities specified for the Week 52/early withdrawal (EW) visit will be performed, c) Oral Lead-in Day 2 PK sample taken between 20 h and 28 h post first oral dose, d) Participants will be asked to collect their temperature daily for 14 days following each injection.

Amendment 3	29-OCT-2020	
Revisions were made to study eligibility criteria, safety assessments and Appendix 8 for participant safety and to further mitigate the potential risks for study conduct during the COVID-19 pandemic and to rephrase sections that were ambiguous. Information on assessments required for sentinel participants in Cohorts 5 and 6 and the definition of what constitutes an overdose of oral cabotegravir have been updated.
 
Revisions pertinent to analysis and reporting include:
 
 • Additional PK samples to be collected on Day 1 (at 8 h and 12 h post dose) during OLI phase for Cohorts 5 and 6 • Weight data to be collected during the follow-up phase

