10.8.3. Vital Signs

Vital Sign Parameter (Absolute)	Units	Clinical Concern Range	
		Lower	Upper
Systolic Blood Pressure	mmHg	<85	>140
Diastolic Blood Pressure	mmHg	<45	>90
Heart Rate (Males)	bpm	<45	>100
Heart Rate (Females)	bpm	<50	>100

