No.	Population	GSK Standard/ Example Shell	Title	Programming Notes	Deliverable [Priority]
2.25.	Safety	SAFE_T1 (See EG1)	Summary of ECG Findings – Part 1 & Part 2–	Unscheduled visits are included for determining worst-case post-baseline	Cohort 1-5, EOS
2.26.	Safety	EG2	Summary of ECG Values – Part 1 & Part 2		Cohort 1-5, EOS
2.27.	Safety	EG2	Summary of ECG Changes from Baseline – Part 1 & Part 2		Cohort 1-5, EOS
2.28.	Safety	SAFE_T2 (See EG10A)	Summary of Maximum QTc Values Post-Baseline Relative to Baseline by Category – Part 1 & Part 2	Unscheduled visits are included for determining maximum QTc values	Cohort 1-5 IA Cohort 1-4, Cohort 1-5, EOS
2.29.	Safety	SAFE_T3 (See EG11)	Summary of Maximum Increase in QTc Values Post-Baseline Relative to Baseline by Category – Part 1 & Part 2	Unscheduled visits are included for determining maximum increase in QTc values	Cohort 1-5 IA Cohort 1-4, Cohort 1-5, EOS
Vital Signs					
2.30.	Safety	VS1	Summary of Vital Sign Values - Part 1 & Part 2		
2.31.	Safety	VS1	Summary of Vital Sign Changes from Baseline – Part 1 & Part 2		Cohort 1-5, EOS
2.32.	Safety	SAFE_T4 (See VS3)	Summary of Vital Sign Results Relative to Potential Clinical Importance (PCI) Criteria Post-Baseline Relative to Baseline – Part 1 & Part 2	Unscheduled visits are included for determination of 'to Low' and 'to High'	Cohort 1-5 IA Cohort 1-4, Cohort 1-5, EOS
Liver Events					
2.33.	Safety	LIVER1	Summary of Liver Stopping Event Reporting – Part 1 & Part 2		Cohort 1-5 IA Cohort 1-4, Cohort 1-5, EOS

Safety: Tables					
No.	Population	GSK Standard/ Example Shell	Title	Programming Notes	Deliverable [Priority]
2.34.	Safety	LIVER10	Summary of Hepatobiliary Laboratory Abnormalities – Part 1 & Part 2	Unscheduled visits are included	Cohort 1-5, EOS
Questionnaires					
2.35.	Safety	SAFE_T5	Summary of Numeric Rating Scale – Part 1 & Part 2	For each period: by visit, maximum and AUC. AUC not needed for Cohort 1-5 IA	Cohort 1-5 IA Cohort 1-4, Cohort 1-5, EOS
2.36.	Safety	SAFE_T6	Summary of Perception of Injection – Part 1 & Part 2		Cohort 1-5 IA Cohort 1-4, Cohort 1-5, EOS
Injection Site Area & Duration by Grade					
2.37.	Safety	SAFE_T7a	Event-Level Summary of Duration (Days) at Each Grade by Injection Site Reaction Preferred Term – Part 1 & Part 2	Injection 1 and Injection 2 periods only. Include pooled treatment groups by dose & route	Cohort 1-5 IA Cohort 1-4, Cohort 1-5, EOS

Safety: Tables					

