No.	Population	GSK Standard / Example Shell	Title	Programming Notes	Deliverable [Priority]
19.	Safety	SAFE_L1	Listing of Details of Injection Site Reaction Adverse Events – Part 1 & Part 2	Include additional variables collected on the impact on social & functional activities forms	Cohort 1-5, EOS
20.	Safety	AE8CPxo	Listing of Serious Adverse Events (Fatal & Non-Fatal) – Part 1 & Part 2		Cohort 1-5 IA Cohort 1-4, Cohort 1-5, EOS
21.	Safety	AE14	Listing of Reasons for Considering as a Serious Adverse Event – Part 1 & Part 2		Cohort 1-5, EOS
22.	Safety	AE8CPxo	Listing of Adverse Events Leading to Treatment Discontinuation and/or Withdrawal from Study – Part 1 & Part 2		Cohort 1-5 IA Cohort 1-4, Cohort 1-5, EOS
COVID-19 Assessment					
23.	Safety	AE8CPxo	Listing of COVID-19 Related Adverse Events – Part 1 & Part 2		Cohort 1-5, EOS
24.	Safety	PAN12	Listing of COVID-19 Assessments and Symptom Assessments for Subject with COVID-19 Adverse Events – Part 1 & Part 2		Cohort 1-5, EOS
25.	Safety	PAN7	Listing of All Subjects with Visits and Assessments Impacted by COVID-19 Pandemic – Part 1 & Part 2		Cohort 1-5, EOS
All Laboratory					
26.	Safety	LB5xo	Listing of All Clinical Chemistry Data for Subjects with any Toxicities – Part 1 & Part 2		Cohort 1-5, EOS
27.	Safety	LB5xo	Listing of All Hematology Data for Subjects with any Toxicities – Part 1 & Part 2		Cohort 1-5, EOS
28.	Safety	LB5xo	Listing of All Coagulation Data for Subjects with any Toxicities – Part 1 & Part 2		Cohort 1-5, EOS

CONFIDENTIAL

212482

ICH: Listings					
No.	Population	GSK Standard / Example Shell	Title	Programming Notes	Deliverable [Priority]
ECG					
29.	Safety	EG5xo	Listing of All ECG Findings for Subjects with an Abnormal Finding – Part 1 & Part 2		Cohort 1-5, EOS
30.	Safety	EG3xo	Listing of All ECG Values for Subjects with Any Value of Potential Clinical Importance – Part 1 & Part 2		Cohort 1-5, EOS
Vital Sign					
31.	Safety	VS4xo	Listing of All Vital Signs for Subjects with Values of Potential Clinical Importance – Part 1 & Part 2		Cohort 1-5, EOS
Liver Event					
32.	Safety	LIVER5	Listing of Liver Monitoring/Stopping Event Reporting – Part 1 & Part 2		Cohort 1-5, EOS
33.	Enrolled	LIVER15	Liver Stopping Event Profile		Cohort 1-5, EOS
Questionnaire					
34.	Safety	SAFE_L3	Listing of Numeric Rating Scale – Part 1 & Part 2		Cohort 1-5, EOS
35.	Safety	SAFE_L4	Listing of Perception of Injection – Part 1 & Part 2		Cohort 1-5, EOS
Immunogenicity					

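### SAP 10.8.3 has no temperature criterion, so a participant whose only abnormal vital sign is fever is not flagged in Table 2.32 or included in Listing 31

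*SAP*

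**What the plan says.** The protocol makes vital signs part of its safety endpoint: "Safety and tolerability parameters including adverse events, clinical laboratory tests, and vital sign assessments" (Protocol 3). Protocol 8.2.2 defines them; they "will include temperature, systolic and diastolic blood pressure, and pulse". Protocol 8.2.6.1, on diary cards, adds: "Participants will also be asked to collect their temperature daily for 14-days following each injection". The amendment history (Protocol 11.10, Amendment 2) gives the reason for this addition as a regulator's comment about collecting temperatures after injection. SAP 1 repeats the requirement among the changes that affect data collection: "Participants will be asked to collect their temperature daily for 14 days following each injection".

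SAP 10.8.3 gives ranges of clinical concern for systolic pressure, diastolic pressure and heart rate (separately for men and women). It has no temperature row. Two displays depend on these ranges: Table 2.32, "Summary of Vital Sign Results Relative to Potential Clinical Importance (PCI) Criteria Post-Baseline Relative to Baseline", and Listing 31, "Listing of All Vital Signs for Subjects with Values of Potential Clinical Importance". Tables 2.30 and 2.31 summarise vital-sign values and changes from baseline without classifying them.

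**The concern.** A planned safety measurement has no route into the displays that pick out abnormal values. Temperature is a protocol vital sign, and extra daily readings were added after a regulator commented on it, but the SAP gives no rule for when a temperature is high.

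Fever after a long-acting injection matters for local infection and for hypersensitivity, and it forms part of the protocol's rash criteria for withdrawal and pausing (Protocol 7.1). Cohort 4h is also the first human use of CAB with rHuPH20 (Protocol 2.3). Without a criterion, the reports will not give a measurement-based count of febrile participants by formulation, route or rHuPH20 use. The count will depend on what was recorded as an adverse event.

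**Working it through.** The plan states no figure to reproduce. The check sets the collected data against the criteria and the displays, then counts clinic and diary days.

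**1. Components against criteria**

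| Vital sign (Protocol 8.2.2) | Range in SAP 10.8.3 |
|---|---|
| Systolic pressure | <85 or >140 mmHg |
| Diastolic pressure | <45 or >90 mmHg |
| Pulse | <45 or >100 bpm (men); <50 or >100 bpm (women) |
| Temperature | none |

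Three of four components have a range. SAP 10.8.1, which grades laboratory values and injection-site reactions, contains no fever grade either.

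**2. Where a high temperature would go**

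- *At a scheduled visit, for example Day 3.* The value contributes to the Day 3 group summaries in Tables 2.30 and 2.31. Table 2.32 has no limit to compare it with. Listing 31 includes the participant only if pressure or heart rate is also out of range.
- *Off schedule, for example an unscheduled visit on Day 11.* The Part 1 vital-sign window for Day 10 spans Days 10 to 12 (SAP 10.3.1), and SAP 10.6.1 keeps the value closest to the target day. If a Day 10 value exists, the Day 11 value leaves the by-visit tables. SAP 10.6.1 sends such values to the worst-case determinations and the listings. For vital signs these are Table 2.32 and Listing 31, the two displays with no temperature criterion.
- *On the diary card only.* No visible table, figure or listing title in SAP 10.10 names temperature, fever or diary data. SAP 10.3 has no window specific to diary readings.

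**3. Deliveries (SAP 10.10.5)**

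Table 2.32 is assigned to the Cohort 1-5 interim, Cohort 1-4, Cohort 1-5 and end-of-study deliveries. Table 2.31 is assigned only to the last two. No delivery is legible for Table 2.30 in the text available. On what can be read, Table 2.32 is the only vital-sign table in the two earlier deliveries.

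**4. Clinic coverage of the 14 days**

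Vital signs are scheduled on Days 1, 2, 3, 5, 6, 7, 8, 10 and 14 (Protocol 1.3; SAP 10.2), which is 9 of 14 days. Cohort 4b adds Day 4, making 10 of 14. Days with a diary reading only are 4 (except in Cohort 4b), 9, 11, 12 and 13.

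**5. Planned maximum of diary entries**

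This assumes every planned injection is given, Cohort 5 receives Injection 1 only and Cohort 6 is not run (SAP 2.3), and diary days are Days 1 to 14.

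- Injections: 80 × 2 + 24 × 2 + 20 × 1 + 22 × 1 = 160 + 48 + 20 + 22 = 250.
- Diary entries: 250 × 14 = 3,500.
- On days with a scheduled clinic reading: 160 × 9 + 48 × 10 + 20 × 9 + 22 × 9 = 1,440 + 480 + 180 + 198 = 2,298.
- On days with the diary only: 3,500 − 2,298 = 1,202, or 34%.

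About two thirds of planned diary entries fall on days that also have a clinic temperature.

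**The case against.** The other side has several good points.

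- **Unclassified is not the same as normal.** A reader might infer that a febrile participant is reported as having no abnormal vital sign. The documents do not support that. The ranges are set per parameter, the shell for Table 2.32 is not available, and with no criterion temperature is simply not classified. This stands, and the point is limited accordingly.
- **Fever can still be reported.** Protocol 11.3.1 makes a clinically significant abnormal vital sign an adverse event. Tables 2.1, 2.6, 2.9 and 2.10 summarise adverse events by preferred term, and Listing 17 lists them all. Clinic temperatures can also feed Tables 2.30 and 2.31. How well those tables would show a few fevers depends on sponsor display standards that are not in the documents. The inference that fever is invisible would be wrong.
- **The rash criteria do not depend on these displays.** They are applied to participants during the study. This stands: the gap concerns reporting, not participant protection.
- **The 3,500 is a ceiling on entries, not a measure of lost information.** It assumes full dosing and compliance, and most of those days also have a clinic reading.
- **The purpose of the diary readings is not stated.** The regulator's comment, as summarised, concerns collecting temperatures. No passage requires a fever rate. Protocol 8.2.6.1 says that concomitant medication goes to the CRF and is silent on temperatures, so the diary may serve only to prompt adverse event reports.
- **Some text is blacked out.** SAP 7.4, parts of SAP 10.6.3 and the titles of Tables 2.41 and 2.43 to 2.48 cannot be read. The shell names and group headings of those tables point to injection-site, questionnaire and preference outcomes, but the statement about displays covers visible ones only.

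None of this supplies a temperature limit for Table 2.32 or Listing 31.

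**Conclusion.** The gap is real and narrow. One of the four protocol vital signs has no criterion of potential clinical importance, so fever alone neither flags a participant in Table 2.32 nor brings one into Listing 31. What remains is adverse event reporting, which relies on the investigator's judgement, and group summaries by visit.

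The conclusion assumes that Table 2.32 and Listing 31 apply SAP 10.8.3 as printed, and that no blacked-out section adds a temperature rule. The study is descriptive and tests no formal hypothesis on its primary PK objectives, so no inferential result is at risk. The consequence is an incomplete display of a stated safety endpoint. The missing criterion is the main point. The missing diary display is secondary, because the documents do not say whether those readings reach the database.

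**What to change.** 1. Add a temperature row to SAP 10.8.3 with an upper limit set by the sponsor, aligned with the DAIDS version 2.1 scale that Protocol 11.7 already adopts for adverse event grading. The visible SAP reproduces no fever grades, so the limit must be written out. Clinic temperatures then feed Table 2.32 and Listing 31.
2. Establish whether the diary temperatures are in the database.
   - If they are, add one table or listing of maximum temperature over Days 1 to 14 per injection, by cohort, formulation and route. Cohort 4h should be shown separately for rHuPH20.
   - If they are not, state in the SAP that they are not analysed and serve only to prompt adverse event reporting.

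The first change costs one criterion row and minor programming. The second costs one display or one sentence. Data entry arises only if the sponsor wants the diary display and the readings are not yet captured. That could then mean retrospective entry of diary cards, since by the Cohort 1-5 interim Cohorts 1 to 3 will have finished follow-up (SAP 3.2). No participant procedure changes.

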10.10.6. Safety Figures

Safety Figures					
No.	Population	GSK Standard / Example Shell	Title	Programming Notes	Deliverable [Priority]
Injection Site Area					
2.1	Safety	SAFE_F1	Plot of Surface Area versus Day Since Injection by Injection Site Reaction Preferred Term – Part 1 & Part 2 (Cohorts 2, 4, 4b , 4h and 5)		Cohort 1-5, EOS

10.10.7. Pharmacokinetic Tables

Pharmacokinetic: Tables					
No.	Population	GSK Standard / Example Shell	Title	Programming Notes	Deliverable [Priority]
PK Concentration Data					
3.1.	Pharmacokinetic	PKCT1	Summary of CAB Plasma Pharmacokinetic Concentration-Time Data (units) – Part 1 & Part 2, Oral Lead-in Phase		Cohort 1-5, EOS
3.2.	Pharmacokinetic	PKCT1	Summary of CAB Plasma Pharmacokinetic Concentration-Time Data (units) – Part 1 & Part 2, Injection and Follow-up Phase		Cohort 1-5 IA Cohort 1-5, EOS
PK Derived Parameters					
3.3.	Pharmacokinetic	PKPT4	Summary Statistics of Derived CAB Plasma Pharmacokinetic Parameters (Non-Transformed) Based on Actual Time by Treatment – Part 1 & Part 2	Parameters with units	Cohort 1-5 IA Cohort 1-5, EOS
3.4.	Pharmacokinetic	PKPT4	Summary Statistics of Derived CAB Plasma Pharmacokinetic Parameters (Ln-Transformed) Based on Actual Time by Treatment – Part 1 & Part 2	Parameters with units	Cohort 1-5 IA Cohort 1-4, Cohort 1-5, EOS
PK Analysis Tables					
3.5.	Pharmacokinetic	PKPT3	Statistical Analysis of CAB Plasma Pharmacokinetic Parameters – Relative Bioavailability		Cohort 1-5 IA Cohort 1-5, EOS
3.6.	Pharmacokinetic	PKPT3	Statistical Analysis of CAB Plasma Trough Concentrations – CAB 400 mg/mL vs. Evaluable Historical CAB 200 mg/mL – Part 1 and Part 2	Historical data from ATLAS/FLAIR	Cohort 1-5, EOS
3.7.	Pharmacokinetic	PKPT3	Statistical Assessment of Dose Proportionality by Route for CAB 400 mg/mL – Injection 1 PK Parameters from Cohorts 1-5 (excluding Cohort 4h)		Cohort 1-5 IA Cohort 1-5, EOS

10.10.8. Pharmacokinetic Figures

Pharmacokinetic: Figures					
No.	Population	GSK Standard / Example Shell	Title	Programming Notes	Deliverable [Priority]
Individual Concentration Data					
3.1.	Pharmacokinetic	PKCF1P	Individual CAB Plasma Concentration-Time Plots by Cohort – Oral Lead-in Phase (Linear and Semi-Logarithmic)	Paginate by Cohort Dashed line represents the LLQ	Cohort 1-5, EOS
3.2.	Pharmacokinetic	PKCF1P	Individual CAB Plasma Concentration-Time Plots by Treatment – Injection and Follow-up Phase (Linear and Semi-Logarithmic)	Paginate by Treatment and Injection Dashed line represents the LLQ	Cohort 1-5, EOS
Mean / Median Concentration Plots					
3.3.	Pharmacokinetic	PKCF2	Mean (\pm Standard Deviation) CAB Plasma Concentration-Time Plots by Treatment – Oral Lead-in Phase (Linear and Semi-Logarithmic)	Treatments Overlaid	Cohort 1-5, EOS
3.4.	Pharmacokinetic	PKCF2	Mean (\pm Standard Deviation) CAB Plasma Concentration-Time Plots by Treatment – Injection and Follow-up Phase (Linear and Semi-Logarithmic)		Cohort 1-5, EOS
3.5.	Pharmacokinetic	PKCF3	Median (\pm Range) CAB Plasma Concentration-Time Plots by Treatment – Oral Lead-in Phase (Linear and Semi-Logarithmic)	Treatments Overlaid	Cohort 1-5, EOS
3.6.	Pharmacokinetic	PKCF3	Median (\pm Range) CAB Plasma Concentration-Time Plots by Treatment – Injection and Follow-up Phase (Linear and Semi-Logarithmic)	Treatments Overlaid	Cohort 1-5 IA Cohort 1-5, EOS

10.10.9. ICH Listings

ICH: Listings					
No.	Population	GSK Standard / Example Shell	Title	Programming Notes	Deliverable [Priority]
Subject Disposition					
1.	Randomized	TA1	Listing of Randomized and Actual Treatments – Part 1 & Part 2		Cohort 1-5, EOS
2.	Screened	ES7	Listing of Reasons for Screen Failure		Cohort 1-5, EOS
3.	Safety	ES2	Listing of Reasons for Study Withdrawal – Part 1 & Part 2		Cohort 1-5 IA Cohort 1-4, Cohort 1-5, EOS
4.	Safety	SD2xo	Listing of Reasons for Study Treatment Discontinuation – Part 1 & Part 2		Cohort 1-5 IA Cohort 1-4, Cohort 1-5, EOS
5.	Safety	BL1	Listing of Subjects for Whom the Treatment Blind was Broken During the Study – Part 1 & Part 2		Cohort 1-5, EOS
Protocol Deviations					
6.	Safety	DV2xo	Listing of Protocol Deviations (Important and/or COVID-19 Related) – Part 1 & Part 2		Cohort 1-5, EOS
7.	Safety	IE3	Listing of Subjects with Inclusion/Exclusion Criteria Deviations – Part 1 & Part 2		Cohort 1-5, EOS
Populations Analysed					
8.	Safety	SP3xo	Listing of Subjects Excluded from Any Population – Part 1 & Part 2		Cohort 1-5, EOS
Demographic and Baseline Characteristics					
9.	Safety	DM2	Listing of Demographic Characteristics – Part 1 & Part 2		Cohort 1-5, EOS
10.	Safety	DM9	Listing of Race – Part 1 & Part 2		Cohort 1-5, EOS
Concomitant Medication and Medical History					

ICH: Listings					
No.	Population	GSK Standard / Example Shell	Title	Programming Notes	Deliverable [Priority]
11.	Safety	CM3xo	Listing of Concomitant Medications – Part 1 & Part 2	Based on GSK Drug Dictionary	Cohort 1-5, EOS
12.	Safety	MH2	Listing of General Medical History – Part 1 & Part 2		Cohort 1-5, EOS
Exposure and Treatment Compliance					
13.	Safety	EX3	Listing of Exposure Data – Part 1	CCI	Cohort 1-5, EOS
14.	Safety	POP_L1	Listing of Drug Accountability for Oral CAB – Part 1 & Part 2		Cohort 1-5, EOS
Adverse Events					
15.	Safety	AE2	Listing of Relationship Between System Organ Class and Verbatim Text		Cohort 1-5, EOS
16.	Safety	AE7	Listing of Subject Numbers for Individual Adverse Events – Part 1 & Part 2		Cohort 1-5, EOS
17.	Safety	AE8CPxo	Listing of All Adverse Events – Part 1 & Part 2		Cohort 1-5 IA Cohort 1-4, Cohort 1-5, EOS
18.	Safety	AE8CPxo	Listing of Injection Site Reaction Adverse Events – Part 1 & Part 2	Include variable from the AE ISR form: “Did the subject use or apply any treatment at home for the injection site related symptom?”	Cohort 1-5, EOS

ICH: Listings					
No.	Population	GSK Standard / Example Shell	Title	Programming Notes	Deliverable [Priority]
19.	Safety	SAFE_L1	Listing of Details of Injection Site Reaction Adverse Events – Part 1 & Part 2	Include additional variables collected on the impact on social & functional activities forms	Cohort 1-5, EOS
20.	Safety	AE8CPxo	Listing of Serious Adverse Events (Fatal & Non-Fatal) – Part 1 & Part 2		Cohort 1-5 IA Cohort 1-4, Cohort 1-5, EOS
21.	Safety	AE14	Listing of Reasons for Considering as a Serious Adverse Event – Part 1 & Part 2		Cohort 1-5, EOS
22.	Safety	AE8CPxo	Listing of Adverse Events Leading to Treatment Discontinuation and/or Withdrawal from Study – Part 1 & Part 2		Cohort 1-5 IA Cohort 1-4, Cohort 1-5, EOS
COVID-19 Assessment					
23.	Safety	AE8CPxo	Listing of COVID-19 Related Adverse Events – Part 1 & Part 2		Cohort 1-5, EOS
24.	Safety	PAN12	Listing of COVID-19 Assessments and Symptom Assessments for Subject with COVID-19 Adverse Events – Part 1 & Part 2		Cohort 1-5, EOS
25.	Safety	PAN7	Listing of All Subjects with Visits and Assessments Impacted by COVID-19 Pandemic – Part 1 & Part 2		Cohort 1-5, EOS
All Laboratory					
26.	Safety	LB5xo	Listing of All Clinical Chemistry Data for Subjects with any Toxicities – Part 1 & Part 2		Cohort 1-5, EOS
27.	Safety	LB5xo	Listing of All Hematology Data for Subjects with any Toxicities – Part 1 & Part 2		Cohort 1-5, EOS
28.	Safety	LB5xo	Listing of All Coagulation Data for Subjects with any Toxicities – Part 1 & Part 2		Cohort 1-5, EOS

CONFIDENTIAL

212482

ICH: Listings					
No.	Population	GSK Standard / Example Shell	Title	Programming Notes	Deliverable [Priority]
ECG					
29.	Safety	EG5xo	Listing of All ECG Findings for Subjects with an Abnormal Finding – Part 1 & Part 2		Cohort 1-5, EOS
30.	Safety	EG3xo	Listing of All ECG Values for Subjects with Any Value of Potential Clinical Importance – Part 1 & Part 2		Cohort 1-5, EOS
Vital Sign					
31.	Safety	VS4xo	Listing of All Vital Signs for Subjects with Values of Potential Clinical Importance – Part 1 & Part 2		Cohort 1-5, EOS
Liver Event					
32.	Safety	LIVER5	Listing of Liver Monitoring/Stopping Event Reporting – Part 1 & Part 2		Cohort 1-5, EOS
33.	Enrolled	LIVER15	Liver Stopping Event Profile		Cohort 1-5, EOS
Questionnaire					
34.	Safety	SAFE_L3	Listing of Numeric Rating Scale – Part 1 & Part 2		Cohort 1-5, EOS
35.	Safety	SAFE_L4	Listing of Perception of Injection – Part 1 & Part 2		Cohort 1-5, EOS
Immunogenicity					
36.	Safety	LB5xo	Listing of All Immunogenicity Data – Part 1		Cohort 1-5, EOS

